2.3 Data Analysis Plan

Statistical Power & Sample Size. Preliminary data for HRV coherence and the pain (BPI), and stress (PSS) scales from our HRV-B pilot study among DVAMC chronic pain patients were used to estimate statistical power for the proposed primary study outcomes (HRV coherence, pain rating, negative emotion, activity limitation, perceived stress scale). Two-sided, two sample t-tests were used for the statistical power calculations. The analysis for the proposed study will use more sophisticated methods that tend to reduce variance in the dependent variables and thus increase power, thus what is presented here is likely conservative. An overall significance level of 0.05 was used with correction for multiple testing via the Bonferroni method for the 5 outcomes (adjusted significance level = 0.01; 0.05/5). Our pilot data indicate that at baseline, no statistical differences were observed between treatment groups for any outcome. The detectable effect differences between treatment and sham groups with corresponding standard deviations are presented in Table 3. We assumed equal variances in the differences between pre- and post-treatment comparisons for both groups. A sample size of 25 in each group will attain a statistical power of at least 84.5% to detect the expected effect differences between treatment groups, and groups sizes of 40 patients will provide statistical power exceeding 95% for comparisons between treatment groups for each outcome. Thus, a sample size of 40 patients per group would achieve ample statistical power even with retentions on of 55-60%.

Table 3. Estimated Power for Differences Between HRV-B Treatment & Sham Interventions

Sample Size per Group	Negative Emotion (4.5±10; 15.5±10)*	Activity limitation (4± 9.5; 14± 9.5)*	Pain Rating (1.8±5.0; 10±5.0)*	Perceived Stress (-1.2±4.5; 4±4.5)*	HRV Coherence (-0.03±0.15; -0.20±0.15)*
22	82.3%	78.1%	99.6%	86.5%	84.9%
25	88.1%	84.5%	99.9%	91.4%	90.2%
30	94.1%	91.7%	99.9%	96.2%	95.4%
40	98.7%	97.9%	99.9%	99.3%	99.1%

*Average pre-post change ± SD in the control group; and average pre-post change ± SD in the treatment group, respectively

Data Quality Control. Data collected by physiological sensors will be encoded and recorded without any identifying information. Analysis and interpretation of data files also will be conducted without reference to any identifying information. Questionnaire data will be labeled using the participant's identification number and will not have personal identifying information anywhere on the form. Once collated, coded questionnaire data will

be entered into a password protected computer for further processing and analysis. We will use the double key entry method of data verification (or equivalent) to help ensure data entry accuracy.

Data Security. Multiple steps will be taken to ensure complete confidentiality of the study data, and confidentiality will be maintained to the fullest extent allowed by law. Data files will be stripped of personal identifiers and replaced with coded participant identification numbers that will be used to link data files from multiple sources (e.g., questionnaires). Once collated, coded data will be entered into encrypted VA workstation computers for further analysis and processing. Data files will be stored on an access-controlled data server (network access to the server is by password for a limited set of study personnel: [name]; <\\v07.med.va.gov\cms\vhacms\[name]> for [name].. To minimize risk of loss of confidentiality, only authorized personnel will have access to research data. Participants will be informed that the local IRB may review de-identified or identified study data. The key linking participant identifiers to the coded data will be maintained by the Contact PI in a locked file cabinet at the DVAMC. Hard copy records with patient identifiers (e.g., signed consent forms) will be maintained in the Contact PI's office at the DVAMC in a locked file cabinet, accessible only to authorized study personnel (Building 106, Hard copies with patient identifiers will be stored in Room E111A). Consultants will not have access to any identifiable data. Data analyses will be performed at the DVAMC using coded data with personal identifiers removed, using coded data via an approved data use agreement with the Department of Epidemiology and Biostatistics, Arnold School of Public Health, University of South Carolina, or using coded data without identifiers via a secure VA Virtual Private Network (VPN) workspace (see below). All study personnel will maintain current VA training requirements (e.g., data security, human subjects protection). If an investigator or research staff member terminates their work on the project, their access to the data will become restricted, and the Information Security Officer will be notified. Data will be maintained in a secure manner until it is no longer needed or until its maintenance is no longer legally required. Data destruction will be performed by deleting electronic files and by shredding paper files.

VINCI Workspace. The VA Informatics and Computing Infrastructure (VINCI) is a Department of Veterans Affairs (VA) Health Services Research & Development (HSR&D) resource center that provides a secure, central analytic platform for performing research and supporting clinical operations activities. It is a partnership between the VA Office of Information Technology (OI&T) and the Veterans Health Administration Office of Research and Development (VHA ORD). VINCI includes a cluster of servers for securely hosting suites of databases integrated from select national VA data sources, as well as statistical software packages for data analysis. VINCI servers for data, applications and virtual sessions are physically located at the VA Austin Information Technology Center (AITC) in Austin, Texas. This secure enclave with 105 high-performance servers and 1.5 petabytes of high-speed data storage has multiple layers of security and disaster recovery to prevent data loss. To ensure the protection of Veteran data, VINCI maintains compliance with the guidelines set forth by Veterans Health Administration (VHA) Handbook 1200.12, Use of Data and Data Repositories in VHA Research, and other applicable VA and VHA policies and regulations. In addition, VINCI has undergone security certification activities in support of obtaining an Authorization to Operate (ATO). Access to VINCI resources are approved in accordance with the requirements of National Data Systems (NDS), VHA Handbook 1200.12, Use of Data and Data Repositories in VHA Research, and all other applicable VA and VHA policies and regulations. All data transferred from VINCI is subject to audit for compliance.

VA-credentialed investigators are granted access to study-specific data along with tools for analysis and reporting in the secure, virtual working environment through a certified VHA network computer within the VA. If not working within a VA or VHA hosted office environment containing VA network access, researchers may apply for and then access VINCI through an approved VPN and Remote Desktop application. The remote computing environment enables data analysis to be performed directly on VINCI servers, offering a number of advantages: uniform security standards for access; a common point of entry for all investigators who use the data; tools for analysis and reporting; tighter and more consistent control of data quality; and the ability to standardize and update terminology and format as technology and methodology improve. Software used for

data analysis in the VINCI workspace, whether provided by VINCI or developed by the study team, will run in remote virtual desktop sessions on VINCI servers within the Austin Information Technology Center.

For this study, coded project specific data without personal identifiers may be uploaded to VINCI servers by secure file transfer protocol as directed by VINCI data managers. Study data maintained on VINCI servers will be kept in accordance with the Department of Veterans Affairs Record Control Schedule 10-1 (RCS 10-1). Data transferred to VINCI servers will be coded using a participant ID number as described above (see [Data Security section](#)) so that none of the data will be personally identifiable. Upon completion of the research project, the study Principal Investigators in conjunction with the VA Information Security Officer (ISO), and in accordance with VA policy, will ensure that, study data will be returned to the DVAMC. The study Principal Investigators have the responsibility for security of study data. Only explicitly authorized study personnel will have access to project data. When study personnel are no longer part of the research team, the study Principal Investigators will amend the data access request to terminate that person's access to all study data and notify the VA Information Security Officer of such action. VINCI data managers and VA OI&T personnel not under the purview of the study Principal Investigators control the servers, network, processors, firewall and software in the VINCI environment, including access rights granted to study personnel. Study specific data stored on VINCI servers will be located at the Austin Information Technology Center, [name]. The specific server where the data are stored within the VINCI environment will be chosen by VINCI personnel. The server name and location within the Austin Information Technology Center may be changed at any time at the discretion of VINCI personnel.

Statistical Analyses. Analysis and interpretation of data files will be conducted without reference to any personal identifying information. We will begin all analyses with an inspection of all variables for completeness, any missing values will be tabulated and range checks will be used to identify observations that need to be validated. Once the data set has been finalized, a locked version will be created to use for all analyses. Descriptive statistics will be applied to questionnaire scores, their potential predictors, demographic and lifestyle variables to evaluate their characteristics and assess their general inter-relationships (e.g., via correlations for numeric measures, or by frequencies among treatment groups for categorical variables). These analyses will provide an understanding of relationships among variables and will aid in planning subsequent analyses. The main analyses pertaining to aims 1 and 2 will consist of linear mixed models for repeated measures data to evaluate the treatment effect on outcomes of interest. We will also implement secondary exploratory path analyses to evaluate direct and indirect effects of the treatment on the primary (HRV coherence, pain, stress), and secondary (insomnia, fatigue, depression, cognition) outcomes.

For each of the outcomes, there will be three measurements per subject (post-training minus pre-training, 4-week booster minus post-training, and 8-week follow-up minus the 4-week booster assessment). To test the effect of HRV-B relative to controls, we will apply linear mixed models for repeated measures data. Models will include the group (intervention or sham), time, and the interaction between group and time as the main independent variables. The effect of the intervention on the outcome could be non-linear in time, thus we will evaluate the inclusion of time as a nominal or ordinal variable and choose the specification that has the best fit in terms of the model assumptions and the BIC statistic. Covariates to be considered in the models include (but are not limited to: age, type and duration of usual pain treatment or medication, or other outcomes that may modify the effect (e.g., stress, pain, sleep). We will use a variable selection procedure to screen and identify all variables that differ among the treatment and control groups (initial selection set at $p < 0.15$), and we will include them in the final statistical model if their inclusion alters the effect estimate for HRV-B by $\geq 10\%$. Linear mixed effect models will be implemented using the PROC MIXED procedure in SAS (v9.3, SAS Institute). The conceptual model of each linear mixed model is:

$$Y_{ij} = \beta_0 + \beta_1 X_{ij} + \beta_2 t_j + \beta_3 X_{ij} \times t_j + s_i + \varepsilon_{ij},$$

where Y is the dependent variable, X is the independent variable of interest (or a vector of covariates), s_i is a subject-specific random effect, and t represents the outcome assessment time points (baseline, follow-up). The β coefficients measure each independent variable's effect. If time is included as an ordinal variable,

significance between treatment and control groups will be tested using Wald tests for appropriate β coefficients. If time is included as a nominal variable, we will use least squared means to test for significant differences between treatment and control groups at each of the post-intervention time points (post-training, booster, 8-week follow-up). In this situation we will use a Bonferroni adjusted alpha level = 0.005 (0.05/10), which results in at least 78% power for all of the outcomes with 25 per group to account for attrition (data not shown).

[figure not shown]
We will use "intention to treat" (ITT) analyses on all subjects without regard to level of compliance. ITT analysis is based on the assumption that once a subject is randomized to a group, data for that subject will enter into the final analysis. ITT assumes unrelated treatment events are equally likely across groups and that outcome data are complete. All data from non-adherent and dropout subjects are included; therefore, ITT provides conservative effect estimates. ITT is most appropriate for randomized, controlled clinical trials involving lengthy treatment protocols when an effective treatment arrests progression of disease. Because recommendations for treatment of primary and secondary outcomes will likely continue to include care (i.e., controls still receive usual care), ITT analysis will better reflect what will be observed if HRV-B is introduced into clinical practice. This analysis answers the question: What is the effect of HRV-B on outcome measures in a situation where individuals range from fully compliant to non-compliant? In this pilot intervention, however, we also are interested in the actual effect of HRV-B on the outcomes. In ancillary analyses, we will perform multiple imputations for subjects with missing data (see below). These *post hoc* analyses will answer the question: What is the effect of full HRV-B training on the outcomes? This will provide a more accurate picture of HRV-B effects because it focuses only on subjects who completed the training.

Missing Data. Inevitably, missing data will arise and a variety of approaches will be considered to address this issue. First, our integrated team will meet and discuss the hypothesized nature of the missingness mechanism.¹⁰⁸ For example, if the subjects have data that are missing completely at random or missing at random (MAR) then multiple imputation (MI) procedures can be used (e.g., "PROC MI").¹⁰⁹ When missingness is suspected to be non-ignorable, then a model for the missingness mechanism must be employed.^{110,111} In all models, sensitivity analyses will be performed to test the robustness of the estimates to the missing data assumption (if any). We will create a number of locked datasets (e.g., 10) with imputed values that will be used in all analyses that require MI. This will ensure that all MI analyses are based on the same imputed data.

Path analysis is a useful statistical tool for modeling how multifaceted processes combine to influence specific outcomes. We will apply path analysis to evaluate the direct and indirect effects of HRV-B on the pain-related study outcomes (pain, stress, fatigue, insomnia, depression) via changes in HRV coherence (Figure 8). This analysis will estimate the direct effect of the intervention on the post-training minus pre-training measurements of the study outcomes. There are three paths that are depicted by the arrows in Figure 8.

The path model will determine the path coefficients, variance explained, and statistical significance of direct and indirect (modifier) effects. Modifiers may include: race, income, lifestyle, duration or quality of hand held stress reliever use, social jetlag, family or work history, physical activity, major life events, coping strategies, or social support. Other paths that consider the influence of modifiers

or confounders will be explored to determine if they improve model fit. PROC CALIS in SAS will be used; satisfactory model parameters will be identified using a Bentler comparative fit index >0.93. This integrated model with appropriate modifiers and mediators will identify variables that contribute to, or detract from, the treatment effect on HRV coherence and pain, stress, fatigue, depression and insomnia. The above SEM is a relatively simple structure with only 6 baseline parameters per outcome, thus with a sample of 60 (30 per

group) the study will have the required minimum number of observations based on the 10:1 rule-of-thumb for sample size with SEMs.¹¹²

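### Holm's step-down procedure would give the same 5% family-wise guarantee as the planned Bonferroni correction and never less power; the gain is about 5 to 10 points on four of the five outcomes at 25 per group, but at most about 2 points at 40

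*Combined protocol and SAP*

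**What the plan says.** In section 2.3 (Data Analysis Plan, Statistical Power & Sample Size) five outcomes are treated as primary for the power calculation: "HRV coherence, pain rating, negative emotion, activity limitation, perceived stress scale". The multiplicity rule there is: "An overall significance level of 0.05 was used with correction for multiple testing via the Bonferroni method for the 5 outcomes", which gives "adjusted significance level = 0.01; 0.05/5". The method is stated as: "Two-sided, two sample t-tests were used for the statistical power calculations". At the attrition case the conclusion is: "A sample size of 25 in each group will attain a statistical power of at least 84.5" percent, and at 40 per group Table 3 shows 97.9% to 99.9%.

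The Statistical Analyses part of the same section gives a different rule, for models that treat time as nominal: "In this situation we will use a Bonferroni adjusted alpha level = 0.005 (0.05/10"). It reports at least 78% power at that level with 25 per group. No adjusted level is given for models that treat time as ordinal. No step-down or other sequential procedure appears anywhere in the document.

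**The concern.** Single-step Bonferroni holds every test to the same fixed level whatever the other tests show. Holm's procedure orders the p-values and compares the smallest with 0.05/5, the next with 0.05/4, and so on up to 0.05, stopping at the first failure. Its first threshold equals Bonferroni's and the later ones are looser. It therefore rejects everything Bonferroni rejects, still controls family-wise error at 5%, and needs no assumption about how the outcomes are correlated.

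The benefit is largest when several effects are real, and Table 3 assumes that all five are. At stake is power on the weaker outcomes if the trial ends nearer 25 than 40 evaluable patients per group, or if the effects are smaller than in the pilot. Both are plausible. The plan defends its sample size under 55–60% retention, which is 22 to 24 of 40 per group. Table 3 rests on a pilot of 8 treated and 6 usual-care patients, whereas this trial's comparator is a sham matched for contact time.

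**Working it through.** **Inputs (Table 3).** Standardised difference = difference in mean change ÷ SD, with equal variances as the plan assumes.
- Negative emotion: (15.5 − 4.5)/10 = 1.10
- Activity limitation: (14 − 4)/9.5 = 1.05
- Pain rating: (10 − 1.8)/5.0 = 1.64
- Perceived stress: (4 + 1.2)/4.5 = 1.16
- HRV coherence: |−0.20 + 0.03|/0.15 = 1.13

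Correlation between outcomes is not in the documents. The range 0 to 0.6 is assumed, with a common value for all pairs.

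**Step 1: reproduce the plan's figures.** For n per group, the noncentrality is d·√(n/2) with 2n − 2 degrees of freedom. For activity limitation at n = 25 this is 1.0526 × √12.5 = 3.72 on 48 degrees of freedom. The two-sided 0.01 critical value is 2.68, and power is 84.5%, as stated. All other Table 3 cells reproduce to within 0.1 point. At the 0.005 level the same outcome has 77.7%, which agrees with the stated 78% after rounding.

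**Step 2: Bonferroni against Holm.** Trials with five correlated normal outcomes were simulated (40,000 to 120,000 per setting). Bonferroni rejects at p ≤ 0.01. Holm uses 0.05/5, 0.05/4, 0.05/3, 0.05/2 and 0.05. All five Table 3 effects are taken as real.

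| Outcome | 25/group, Bonferroni | 25/group, Holm (correlation 0 / 0.5) | Gain, points | 40/group gain, points |
|---|---|---|---|---|
| Activity limitation | 84.5% | 94.8% / 93.7% | 10.3 / 9.2 | 1.7 / 1.8 |
| Negative emotion | 88.1% | 96.4% / 95.2% | 8.0 / 7.0 | 1.1 / 1.0 |
| HRV coherence | 90.2% | 97.1% / 96.0% | 6.8 / 5.9 | 0.7 / 0.7 |
| Perceived stress | 91.4% | 97.6% / 96.4% | 6.0 / 5.0 | 0.6 / 0.6 |
| Pain rating | 99.9% | over 99.9% / 99.9% | 0.1 / 0.0 | 0 / 0 |

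At correlation 0.6 the gains at 25 per group are 8.9 (activity limitation), 7.0 (negative emotion), 5.5 (coherence) and 4.6 (stress). At 22 per group, the lower end of the plan's retention range, the gain is 11 to 13 points on activity limitation and 9 to 11 on negative emotion.

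**Step 3: vary the truth.**
- *Smaller effects.* At 40 per group with 75% of the Table 3 effects, activity limitation rises from 81% to 91–93% and negative emotion from 85% to 93–95%. That is a gain of about 8 to 12 points on these two.
- *Fewer real effects* (25 per group, correlation 0.5). If only negative emotion and activity limitation respond, the gain on them is 1.3 and 1.6 points. If pain also responds, it is 3.1 and 3.8.

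**Step 4: error rate.** With all five nulls true the two methods give the same family-wise error, because their first step is identical. With only activity limitation null and the other four effects real (correlation 0.3), family-wise error is 1.0% for Bonferroni and 4.5% (25 per group) or 4.9% (40 per group) for Holm. Both stay within 5%.

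**Step 5: the analysis-stage rule.** The nominal-time analysis compares groups at post-training, booster and 8-week follow-up. Five outcomes × 3 time points = 15 tests, not 10. With 15 tests at 0.005 each, the Bonferroni bound on family-wise error is 15 × 0.005 = 0.075. If the 10 is read as five outcomes × two time points (an assumption, with persisting effects and within-outcome correlation 0.6), Holm gains 11 to 16 points on the two weakest outcomes at 25 per group and 2 to 3 at 40.

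**The case against.** The strongest reply is that little is lost under the plan's own main case. At 40 per group with Table 3 effects, power already exceeds 97% on every outcome, and the gain is at most about 2 points. That stands. A reader might infer that some 8 to 10 points are given away in any event. The figures support that size only for the two weakest outcomes, and only at about 25 evaluable per group with all effects real, or at 40 per group with smaller effects.

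The endpoints named in the Specific Aims are coherence, pain and stress, and the largest gains fall elsewhere, on negative emotion and activity limitation. That also stands, although coherence and stress still gain 5 to 7 points at 25 per group.

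A reader might infer that the trial's chance of success is reduced. The documents do not support this. They nowhere require all five outcomes to be significant, and the chance of at least one rejection is the same under both methods by construction.

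A reader might also infer that the extra power costs nothing in error. Step 4 shows that when some nulls are true Holm uses more of the 5% allowance, without exceeding it.

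It can further be said that 0.01 belongs to the power calculation and is not shown to govern the analysis. That is correct. The only adjusted level in the analysis text is 0.005, and it applies only if time is nominal.

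Finally, Bonferroni gives simple matching simultaneous confidence intervals and Holm does not. This is a real, small drawback.

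**Conclusion.** The point holds as a cheap efficiency improvement. Single-step Bonferroni is a valid choice for a correctly counted family, so reading it as a statistical error goes beyond what the plan shows. Holm dominates it on power at the same 5% guarantee under any dependence.

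The size of the gain depends on three conditions: the number of evaluable patients, how many effects are real, and how large they are. The sizes also rest on the plan's two-sample t-test framework, normal outcomes with equal variances, and the assumed correlation range. The planned mixed model was not simulated.

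One related matter needs settling for either method: until the family of tests is defined, 5% control is not assured at the analysis stage.

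**What to change.** 1. In the Statistical Analyses part of section 2.3, list the primary tests explicitly: which outcomes, which time points or contrasts, and how many in total. State the family for both the nominal and the ordinal specification of time, and reconcile the divisor of 10 with the 15 comparisons that the text implies.
2. In both places in section 2.3, replace the single-step correction with Holm's step-down procedure at family-wise 0.05 over that family, and report Holm-adjusted p-values.
3. Keep Table 3, described as a lower bound on power for the five-test family. Recompute the 78% figure if the listed family is not 10 tests, because a larger family makes Holm's first threshold stricter than 0.005.
4. Report ordinary 95% intervals beside the adjusted p-values and label them unadjusted, since such an interval can exclude zero while the Holm-adjusted p-value exceeds 0.05.

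The cost is a sentence in each place plus the list of tests. It needs no new data or patients. The change should be made before outcome data are analysed.

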1.1. Preliminary Studies

We are now conducting a randomized, single blind, sham-controlled study funded by the Department of Defense (DoD) to examine the effectiveness of HRV-B in alleviating PTSD symptoms. Three groups of combat veterans are being studied: (1) PTSD patients who received active HRV-B training (n=30); (2) PTSD patients who received sham HRV-B training (n=30); and (3) Veterans without PTSD who were assessed only at baseline and received no HRV-B training. Training lasted six weeks. Participants were assessed Pre-training, immediately Post-training, and 8 weeks after training. To date, 73 participants have been enrolled, with 32 assigned to the Sham group, 29 to the active Biofeedback group, and 12 to the Control group. Data analysis is ongoing and results are being prepared for submission for review for publication.

Effect of HRV-B on HRV Coherence. In this ongoing study, the time domain variable RMSSD was used as an

[figure not shown]

indicator of coherence because it correlates very highly with vagal tone and parasympathetic output ($r=0.853$, $p<0.001$).^{52,53} Linear mixed model analysis of RMSSD for Group (Sham vs. HRVB) x Time Period of Assessment (Pre-, Post-, Follow-up) showed that the interaction effect was significant, $F(5, 125)=2.50$, $p=.034$. Follow-up testing of the interaction effect revealed that the Group main effect was statistically significant, $HRV-B > Sham$, $60.2 (43.6)$ vs. $46.1 (37.3)$, $F(1,127)=4.66$, $p=.033$. Contrasts within the HRV-B group revealed that Pre-training RMSSD was statistically lower than combined Post-training and Follow-up, $44.1 (22.8)$ vs. $72.6 (51.4)$, $t(57)=-2.58$, $p=.013$, but Post-training was not

statistically different from Follow-up, $74.8 (63.2)$ vs. $69.7 (32.8)$, $t(57)=0.346$, $p=.730$. In summary, active HRV-B increased HRV coherence and the increase persisted until the Follow-up period (Figure 3).

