2.0 STUDY DESIGN AND METHODS

Overview. The proposed intervention will use a previously approved, standardized HRV-B training protocol.⁴⁴ The primary (HRV coherence, pain, stress) and exploratory outcomes (insomnia, fatigue, depression, cognition) will be assessed at baseline, after the 6 weekly treatments, at the 4-week post-training booster, and at the 8-week post-training follow-up. Standardized procedures will characterize HRV coherence and other frequency- or time-domain HRV measures, and validated instruments will be used to assess pain^{64,65} and

stress.⁶⁶ Sham intervention subjects will have pulse and respiration monitored but not receive active training; instead they will view a static, relaxing nature picture on a computer screen. We will provide portable data-logging devices for practicing HRV-B at home, and sham devices. Wrist actigraphy will characterize insomnia via continuous, 24-hour/day personal monitoring of rest/activity rhythms at 1-week intervals coinciding with the baseline, post-training, and 8-week follow-up assessments only.^{58,67-69}

Data analyses will test for differences in primary and secondary endpoints at baseline, after 6 weeks of active versus sham HRV-B treatment, at the 4-week post-training booster/assessment, and 8 weeks after training. Analyses will be based on intent to treat with two-sided tests. The effect of HRV-B on coherence and other HRV variables will be analyzed using linear mixed models for repeated measures data from sequential time assessments, and a between-subjects factor to evaluate the intervention after adjusting for potential confounding factors (e.g., age, standard therapy, medications, co-morbid disease). Baseline relationships between HRV coherence and endpoints will be examined using multiple regression models. Few studies have examined the multivariate relationship between pain, autonomic dysfunction, stress, depression, sleep, rest/activity rhythms, fatigue, and cognition. Path analyses will be used to model interrelationships between HRV-B, primary and exploratory outcomes, and behavioral or social factors that facilitate the persistence of HRV coherence and pain management effectiveness.

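### The plan describes the mixed model's dependent variable in two ways that cannot both hold, so what the booster and 8-week tests estimate is unsettled

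*Combined protocol and SAP*

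**What the plan says.** The Statistical Analyses text in section 2.3 introduces the data for each outcome as "three measurements per subject (post-training minus pre-training, 4-week booster minus post-training, and 8-week follow-up minus the 4-week booster" assessment, and the next sentence applies the linear mixed model. The opening summary lists the same three changes, directly after saying that the repeated-measures models will address both the treatment effect and its persistence.

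The model has group, time and their interaction, with a subject random effect. The dependent variable is not identified as a score or a change. On the time variable, section 2.3 says that "t represents the outcome assessment time points (baseline, follow-up" are its values.

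Time may enter as ordinal or nominal; the team will "choose the specification that has the best fit in terms of the model assumptions and the BIC statistic". With ordinal time, "significance between treatment and control groups will be tested using Wald tests for appropriate" coefficients, which are not named. With nominal time, "we will use least squared means to test for significant differences between treatment and control groups at each of the post-intervention time points", listed as post-training, booster and 8-week follow-up. These tests use alpha 0.005, "which results in at least 78% power for all of the outcomes with 25 per group".

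The overview in section 2.0 says: "Data analyses will test for differences in primary and secondary endpoints at baseline, after 6 weeks of active versus sham HRV-B treatment", and then at the booster and 8 weeks after training. Section 2.4 sets HRV and questionnaire collection at four visits, T-1 to T-4.

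**The concern.** The two descriptions do not fit one dependent variable. Visit scores have a value at baseline; consecutive changes do not. For a consecutive change, the booster entry is T-3 minus T-2 and the 8-week entry is T-4 minus T-3. A group difference in either shows whether the arms moved apart or together since the last visit. It does not show whether they differ at that visit, which is how the nominal-time tests are worded.

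What is at stake is the reading of the booster and 8-week results, and so of persistence, which the summary assigns to these models. An analyst who follows the consecutive-change sentence could report a lasting benefit as no group difference at both later visits, or a benefit that has merely worn off as a result favouring sham. No section says which description governs.

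**Working it through.** **Inputs.** From Table 3, the least-powered outcome is activity limitation: mean pre-post change 4 in control and 14 in treatment, SD 9.5 in each arm. So D = 14 - 4 = 10. The Table 3 footnote confirms that these are pre-post changes. Tests are two-sided two-sample t-tests. Alpha is 0.01 (0.05/5) for Table 3 and 0.005 (0.05/10) for the nominal-time tests. The group size is 25. The documents give no booster or 8-week effect, and no SD for T3-T2 or T4-T3.

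**Formula.** Noncentrality = D / (SD × √(2/n)), with 2n - 2 = 48 degrees of freedom. Power comes from the noncentral t distribution.

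**Step 1: reproduce the plan's figures.** For activity limitation, noncentrality = 10 / (9.5 × √(2/25)) = 3.72.

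| Outcome, 25 per group | Table 3 | Recomputed, alpha 0.01 | Recomputed, alpha 0.005 |
|---|---|---|---|
| Negative emotion | 88.1% | 88.1% | 82.2% |
| Activity limitation | 84.5% | 84.5% | 77.7% |
| Pain rating | 99.9% | 99.9% | 99.7% |
| Perceived stress | 91.4% | 91.4% | 86.6% |
| HRV coherence | 90.2% | 90.2% | 84.9% |

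The minimum at alpha 0.005 is 77.7%, which rounds to the stated 78%. That figure is therefore the pre-post change calculation.

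**Step 2: a benefit that is fully maintained.** The expected group differences in score at T-1 to T-4 are 0, D, D, D.

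- Change from T-1 at T-2, T-3, T-4: D, D, D.
- Consecutive change: D - 0 = D; D - D = 0; D - D = 0.

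With consecutive changes and nominal time, the post-training test has 77.7% power, while the booster and 8-week tests reject at 0.5% each. Those two values equal alpha whatever the SD, because the expected difference is zero. With change from T-1, and SD 9.5 assumed at each visit, power is 77.7% at all three.

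**Step 3: a benefit held to the booster and lost by week 8.** The expected group differences in score are 0, D, D, 0. Change from T-1 gives D, D, 0. Consecutive change gives D, 0, -D. The week-8 test then points against HRV-B although the arms are equal at that visit. How often it is significant depends on the SD of T4-T3, which has to be assumed (D = 10, 25 per group, alpha 0.005):

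| Assumed SD of T4-T3 | Noncentrality (absolute value) | Significant against HRV-B |
|---|---|---|
| 7 | 5.05 | 97.9% |
| 9.5 (Table 3 pre-post value carried over) | 3.72 | 77.7% |
| 12 | 2.95 | 50.7% |

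**Step 4: what is unaffected.** The first consecutive change, T2-T1, is the change from baseline at post-training. That contrast, which Table 3 powers, is identical under the two change definitions.

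**The case against.** The strongest reply is that the plan is clear enough. The same three consecutive changes are listed in both the summary and section 2.3, while the mention of baseline is a parenthesis attached to what is called a conceptual model. Labelling each change by the visit that ends its interval fits everything else in that part of section 2.3. The overview sentence in section 2.0 could be a comparability check. The earlier mixed model in section 1.1, with "Group (Sham vs. HRVB) x Time Period of Assessment (Pre-, Post-, Follow-up" as its factors, belongs to a different study in PTSD and does not define this one. This has force: the documents do not establish that visit scores were intended. But the parenthesis remains unexplained, and nothing reconciles it.

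A second reply is that consecutive changes are a fair measure of persistence. No difference in T3-T2 is what maintenance looks like, and an adverse T4-T3 correctly signals loss. That stands, provided the result is labelled as change since the previous visit. The plan instead presents it as a difference between arms at the visit.

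A reader might also infer that the ordinal-time option would report a maintained benefit as a declining one. The documents do not support that. The tested coefficients are left open, and the model includes group as well as the interaction. With consecutive changes the average group effect is (D + 0 + 0)/3 = D/3. Under equal correlation between visits, the average change (T4 - T1)/3 has SD 9.5/3, so the standardised effect is again 10/9.5 and power at alpha 0.01 is 84.5%. Moreover, change from T-1 gives D, D, D, whose slope is also zero for a maintained benefit.

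Finally, all four visits are collected, so status at booster and week 8 stays recoverable. That limits the harm to what is tested and reported.

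**Conclusion.** The inconsistency is real and should be fixed. If the consecutive-change sentence is followed with nominal time, the booster and 8-week tests do not estimate the effect at those visits: a maintained benefit is rejected at 0.5% at each. This result needs no SD assumption. A benefit lost between booster and week 8 appears as -D, significant against HRV-B in about 51% to 98% of trials. That range rests on D = 10, 25 per group, alpha 0.005 and an assumed SD from 12 down to 7.

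The harm is confined to the booster, 8-week and persistence conclusions. A reader might infer that the 78% power figure is wrong or that the main post-training result is compromised; neither follows. The 78% reproduces as 77.7% from pre-post changes. It carries to the later visits only for change from baseline, with the effect retained and the same SD.

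**What to change.** - Reconcile the summary, section 2.0 and section 2.3 by naming one dependent variable: either visit scores at T-1 to T-4, or change from T-1 at T-2, T-3 and T-4.
- Define the treatment effect at each post-training visit as the group contrast in change from baseline.
- Keep T3-T2 and T4-T3 only as secondary contrasts, labelled as change since the previous visit.
- If ordinal time remains an option, name the coefficient that is the treatment effect and the alpha at which it is tested.
- State which contrast the 78% covers, and under what assumptions about the retained effect and the SD.

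The cost is SAP wording and a few lines of PROC MIXED code. No new data are needed.
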